6. TARGET POPULATION

6.1. Eligibility

The target group for this research is the population of households at risk of homelessness within the next 3-6 months, across the four LAs participating in this trial (see **5.3 Research Setting**).

Eligibility criteria

Households will be deemed 'at risk' according to a predictive model run by Xantura. The model generates a household-specific risk score (0-100) indicating the expected likelihood of the household becoming homeless in the next three to six months under BAU conditions. Any household with a score greater than or equal to 50 is considered 'at risk' and is eligible for the trial unless they meet one of the exclusion criteria set out below.

Exclusion criteria

Households who meet any of the following exclusion criteria will not be eligible, regardless of risk score:

- They are already participating in a CHI trial
- They ask not to receive the intervention
- They ask for their data not to be used in this trial
- They are already receiving intensive support from LAs via a Relief or Prevention Duty issued in the last 6 months

- They have already been identified in OneView by London Borough of Barking and Dagenham's Homes and Money hub and are receiving targeted support (this team is already using the OneView model to provide targeted support)

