8.2. Retention strategies

Given that the recruitment and assessment processes are driven by administrative data, and that the intervention does not require ongoing compliance on behalf of the household contacted by the LA, retention is not expected to be a significant challenge in this evaluation.

In order to promote engagement with the intervention, a lead adult of each household in the intervention arm will receive a pre-notification text message alerting them to the fact that they will receive a phone call from their LA. Households in the control arm will not be notified that they are included in the trial.

There are no additional incentives offered to participants for participation in this trial.

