9.2. Attrition Assumptions

We conducted power calculations prior to confirmation of the final list of participating councils. When doing this, we considered the following scenarios:

Scenario A (our planned main scenario) – Five LAs take part; 500 households recruited and randomised per LA, with 20% lost as post-randomisation attrition. Achieved n = 2,000.

Scenario B – as Scenario A, but the recruited sample in Batches 2 and 3 are reduced by 20% due to delivery constraints that become apparent in Batch 1. Achieved n = 1,736.

Scenario C – as Scenario A but one of the five LAs withdraws before the start of the trial. Achieved n = 1,600.

RBKC withdrew before the start of the trial (December 2024), so Scenario C will represent the expected main scenario at the time this protocol is first registered.

Scenario D – as Scenario B but one of the five LAs withdraws before the start of the trial. Achieved n = 1,388.

The attrition assumption covers participants opting their data out of the evaluation, gaps in administrative records, or participants moving out of the LA during the trial period. We expect such instances to be few, so the figure of 20% is likely to be conservative. It was arrived at by CHI early in the trial's development and has been maintained in the absence of strong evidence justifying amending it. Note that its impact is minor – adjusting assumed attrition in Scenario A from 20% to 5% changes the range of MDES from 2-7pp to 2-6pp.

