10.8. Missing data

Description of Missing Data Patterns

The trial's reliance on existing administrative data means the risk of data being missing on a large scale is generally low. The predictor variables in our specified

analyses must be present for a household to be enrolled in the trial, so the only variables in which missing data should be possible are our outcome measures. We will describe the extent of missingness of all primary and secondary outcomes; overall, by arm, and in each LA.

Following CHI's Statistical Analysis Guidance, in the event of any missing data we will seek to establish why (the mechanism) and the pattern of missingness. To do so, we will run a binary logistic regression to regress an indicator of missingness on the treatment dummy variable and blocking variables used in our primary analysis. A statistically significant effect of treatment would indicate that data are 'missing experimentally not at random' (MENAR), i.e., there is evidence of differential loss of data across the trial's arms, which might be a source of bias.

If any of the blocking variables are statistically significant, then the data is not 'missing completely at random' (MCAR). The blocking design used in the randomisation balances treatment and control across LAs and levels of predicted baseline risk, so evidence that outcomes are not MCAR is not necessarily indicative of bias. In this case, we would re-run the primary analysis without the blocking variable and if the results are similar then a complete-case analysis is unlikely to be biased.

Handling Missing Data

For less than 5% missingness overall in our primary/secondary outcome we propose a complete-case analysis. Likewise, if the treatment dummy variable is not significant then data are 'missing experimentally at random' (MEAR) and a complete case analysis is appropriate.

Where outcomes are MENAR, we will explore several methods to reduce bias. The imputation methods preferred in CHI's guidance are not possible, since they depend on baseline measures that won't be present in this study. Instead, we will trial and report on each of the following:

- Excluding any blocks containing missing data from the primary analysis
- Introducing additional household-level covariates to see if conditioning on them eliminates the statistically significant effect of treatment on the likelihood of missingness, and then repeating the primary analysis with those covariates included.

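### The complete-case rule in 10.8 ignores which arm the missing outcomes come from, although data opt-out is likely to be one-sided, and 6.1 lists opt-outs prompted after randomisation as eligibility exclusions

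*Protocol*

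**What the plan says.** **Missing outcomes (10.8).** There are two routes to a complete-case analysis. The first is a threshold: "For less than 5% missingness overall in our primary/secondary outcome we propose a complete-case analysis". The second is a significance test: "if the treatment dummy variable is not significant then data are 'missing experimentally at random' (MEAR) and a complete case analysis is appropriate". The same section plans diagnostics with no lower limit: "in the event of any missing data we will seek to establish why (the mechanism) and the pattern of missingness", for which "we will run a binary logistic regression to regress an indicator of missingness on the treatment dummy variable" and on the blocking variables. It also promises description: "We will describe the extent of missingness of all primary and secondary outcomes; overall, by arm, and in each LA". If treatment is significant, several remedies follow, including imputing all missing outcomes as 1 or all as 0. The section does not say which rule governs when missingness is below 5% and treatment is significant.

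**Who learns of the opt-out.** Section 8.2: "Households in the control arm will not be notified that they are included in the trial". Under 6.3 and 15.2, treatment households receive a text linking to the Privacy Notice before their call, which is after allocation. Under 3.1, call handlers have guidance on offering opt-out from the service and the study. Section 16.3 words the right to withdraw for participants generally and says the notice will be on the funding ministry's website.

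**How opt-outs are classed.** Section 6.1 lists "They ask not to receive the intervention" as an exclusion criterion, with a second for households that refuse use of their data. Section 9.2 instead treats data withdrawal as loss after randomisation: "The attrition assumption covers participants opting their data out of the evaluation". Section 10.1 analyses all randomised households with a primary outcome, and 10.3 states an intention-to-treat basis.

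**The concern.** An overall threshold is a reasonable shortcut when losses arise in the same way in both arms. Here one cause of loss, data withdrawal, is prompted directly in the treatment arm alone and depends on household behaviour. That is the loss that can bias a randomised comparison, and a threshold on the total cannot see it. If households that withdraw differ in risk from those that stay, the primary estimate compares a selected treatment arm with a complete control arm.

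The wording of 6.1 adds a second difficulty. If a household that declines the call after randomisation can be called ineligible, it might be removed from the comparison and never enter the missingness count in 10.8.

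**Working it through.** **Inputs from the protocol.** Equal allocation (5.2). Target of 500 households per local authority (6.2). Test Valley is left out of the primary analysis (5.2, update), so 3 × 500 = 1,500 randomised households, 750 per arm. With all four authorities, 2,000, or 1,000 per arm (Table 7, Scenario C). Two-sided alpha 0.05, power 0.80.

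**The plan's own figure.** Scenario C: 2,000 × (1 − 0.20) = 1,600, or 800 per arm. At 80% power the detectable difference is 6.98 points at a 50% base rate and 1.97 points at 3%. The stated 2-7 points is reproduced.

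**Step 1: the largest one-arm loss under the 5% rule.** Take the largest whole number below 5% of N, all in one arm.
- N = 1,500: 74 missing; 74/1,500 = 4.93% overall; 74/750 = 9.9% of the treatment arm.
- N = 2,000: 99 missing; 99/2,000 = 4.95% overall; 99/1,000 = 9.9%.

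An exact by-arm test reacts long before this: 6 missing against 0 gives Fisher p = 0.031 at either size.

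**Step 2: the significance route when no control outcome is missing.** Logistic regression of missingness on treatment alone, 750 per arm:

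| Missing, treatment v control | Overall | Wald p | Likelihood-ratio p | Fisher p |
|---|---|---|---|---|
| 60 v 0 | 4.0% | 0.999 | 2e-20 | 5e-19 |
| 80 v 0 | 5.3% | 0.999 | 6e-27 | 2e-25 |
| 60 v 1 | 4.1% | 4e-5 | 2e-18 | 2e-17 |
| 80 v 1 | 5.4% | 8e-6 | 8e-25 | 8e-24 |

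In the zero-control rows the model is separated: the coefficient is about 24 and its standard error about 13,000. The 80 v 0 row lies above 5%, where only the significance route is left. Read by its Wald p-value, 10.8 would call that loss unrelated to treatment and accept complete-case analysis. One missing control outcome, or another test, removes the fault.

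**Step 3: possible bias (assumptions, not protocol figures).** Bias = share of the treatment arm lost × risk gap between those who stay and those who withdraw. Take no true effect, a 50% base rate and 600 per arm (three authorities after 20% attrition). Standard error = √(2 × 0.25/600) = 2.89 points.

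| Share lost | Gap (points) | Bias (points) | False rejection at two-sided 5% |
|---|---|---|---|
| 8% | 20 | 1.6 | 8.6% |
| 8% | 30 | 2.4 | 13.2% |
| 8% | 40 | 3.2 | 19.8% |
| 10% | 20 | 2.0 | 10.7% |
| 10% | 30 | 3.0 | 18.0% |
| 10% | 40 | 4.0 | 28.3% |

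As a check with arm sizes that fit under 5% overall loss, take 676 of 750 treated and all 750 controls. With a true arm rate of 50% and a rate q among those lost, bias = (0.5 − 0.0987q)/(1 − 0.0987) − 0.5. For q = 40% this is 1.1 points (7.0% false rejection). For q = 25% it is 2.7 points (17.8%). The sign reverses if those who withdraw are at higher risk.

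**Step 4: the sections side by side.** A household that is not told of the study before randomisation has no prompt to object before it. Section 6.1 makes the objection a bar to eligibility; 9.2 counts a data objection as attrition; 10.1 and 10.3 keep every randomised household with an outcome. For a household that declines only the call, 6.1 and 10.1 point in opposite directions.

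**The case against.** A reader might infer that a one-arm loss below 5% would go unchecked. The protocol does not support that. The missingness regression applies to any missing data, and missingness will be reported by arm, so a 74 to 0 split would be displayed. What remains is narrower: nothing makes a significant result override the under-5% route.

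A reader might also infer that controls cannot opt out. Section 16.3 gives the right to participants generally, and the notice is public. The imbalance is in direct notice and therefore in likely practice, not in entitlement.

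The separation fault is fragile. It needs no missing control outcome from any cause, while 9.2 names record gaps and moves out of the area, which can occur in either arm. The protocol does not name a Wald test. Both points stand, so this is a trap to close and not an expected failure.

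On eligibility, 6.2 applies the criteria when each batch is drawn, no section says that decliners are dropped after randomisation, and 10.6 already makes a household without a completed call non-compliant. That makes the conflict one of wording, but the wording still allows two readings. A household may also object before a later batch is drawn, so deleting the criteria outright would go too far.

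Finally, 9.2 expects few such losses, and no opt-out rate or risk gap is given. The 9.9% is a ceiling.

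**Conclusion.** The point holds in limited form. The overall 5% rule permits up to 9.9% loss in treatment with none in control, in a design where notice of opt-out is one-sided, and 10.8 does not say that evidence of differential loss takes precedence. Above 5%, the significance rule can give a false all-clear, but only with zero control losses and a Wald test. The eligibility wording in 6.1 conflicts with 9.2, 10.1 and 10.3 for requests made after randomisation.

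The actual bias cannot be known from the protocol. The 1.6-4 points and 9-28% false rejection rest on an assumed 8-10% one-arm loss, a 20-40 point risk gap, a 50% base rate and 600 per arm. They show that the ceiling matters against a stated detectable difference of 2-7 points; they are not a forecast. If withdrawals are as few as expected, the effect will be small.

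**What to change.** 1. **Section 6.1.** Limit the two opt-out exclusions to requests made before randomisation. State that a household that declines the call after randomisation without withdrawing its data stays in the intention-to-treat set and is non-compliant in the complier analysis, and that data withdrawals after randomisation count as missing outcomes in their arm.
2. **Section 10.8.** Replace the overall-5% and non-significance waivers. Report missingness by arm with the risk difference and an exact or likelihood-ratio test. Whenever data are withdrawn or loss differs by arm, including below 5% overall, report the all-1 and all-0 imputations already planned. For one-arm loss these are the extreme bounds; if both arms lose data, add bounds that impute the arms in opposite directions.

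The cost is wording and a few model runs. Section 13.2 already provides for an addendum before analysis. The bounds may make the conclusion less definite: their width equals the share lost, so 6 of 750 adds 0.8 points and 74 of 750 adds 9.9 points.

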9. SAMPLE SIZE AND POWER CALCULATION

9.1. Sample Size / Power Calculation

There is little evidence at present for the likely scale of any treatment effects, or for the distribution of baseline risk scores in each participating LA or how well they really predict future homelessness. Each of these could impact power. Furthermore, the sample size is limited by the number of at-risk households in the population and LAs' capacity to deliver the treatment, of which we expect the latter to be more limiting. We therefore start here from the planned sample size that LAs initially consented to when they agreed to take part (500 per LA) and consider the implications of various scenarios in which the achieved sample is lower than planned due to delivery constraints or attrition (e.g., missing data), under a set of conservative assumptions.

We present below the Minimum Detectable Effect Size (MDES) for effect of treatment on the (binary) primary outcome measure under each scenario. MDES are shown as absolute percentage point differences, provided as ranges because they vary depending on baseline proportions. To minimise the risk that our power calculations overstate power, we make the conservative assumption that the planned baseline covariates do not account for any variance in the primary outcome. This is in practice unlikely to be the case, although they may not greatly improve power if baseline risk scores are high in most sampled households.

Under our assumed likely scenario, our MDES at alpha = 0.05 and power (beta) = 0.8 is a 2-7 absolute percentage point difference in the proportion of households becoming homeless between treatment and control. Ranges are provided because the MDES expressed in absolute terms varies with base probability of homelessness under the null hypothesis (Figure 3).

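### Section 10.8 takes a non-significant treatment term in the missingness regression as showing that loss is ignorable, and runs its imputation and extreme-value analyses only when that term is significant

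*Protocol*

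**What the plan says.** Protocol section 10.8 sets three steps for missing outcomes.

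- **Description.** "We will describe the extent of missingness of all primary and secondary outcomes; overall, by arm, and in each LA".
- **Test.** The evaluators will "regress an indicator of missingness on the treatment dummy variable and blocking variables used in our primary analysis". A significant treatment term is labelled MENAR. A significant blocking variable leads to a different check: "In this case, we would re-run the primary analysis without the blocking variable".
- **Handling.** "For less than 5% missingness overall in our primary/secondary outcome we propose a complete-case analysis". Then: "Likewise, if the treatment dummy variable is not significant then data are 'missing experimentally at random' (MEAR) and a complete case analysis is appropriate". The remedies follow under a condition: "Where outcomes are MENAR, we will explore several methods to reduce bias". They are excluding blocks with missing data, adding covariates, imputing from the same block, and setting all missing outcomes to 1 or all to 0.

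The rule on a non-significant treatment term has no ceiling on total loss and no margin or confidence limit for the difference between arms. Section 10.1 limits the analytic sample to households with the primary outcome. None of the sensitivity analyses in section 10.6 deals with missing outcomes.

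On the sources of loss, section 9.2 says: "The attrition assumption covers participants opting their data out of the evaluation, gaps in administrative records, or participants moving out of the LA". It plans for 20% loss and calls that figure likely to be conservative.

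**The concern.** The rule draws a positive conclusion, that loss is ignorable, from a test that failed to reject. Two problems follow.

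1. A non-significant treatment term is compatible with a real difference in loss between arms, and increasingly so as total loss rises, because the standard error grows.
2. The regression contains treatment and blocking variables only. The missing outcome cannot be a term in it, so it cannot see whether loss depends on the outcome differently in the two arms.

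Different mechanisms by arm are plausible here. Section 8.2 says controls are not told that they are in the trial. Treatment households receive a link to the Privacy Notice (section 6.3), and call handlers are guided to offer an opt-out from the study (section 3.1). Moving out of the area may be related to homelessness.

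At stake is whether the analyses that could show sensitivity to missing outcomes are run at all. If the test is non-significant, the primary result is reported with complete case declared appropriate, even at 20% loss.

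**Working it through.** **Inputs from the protocol.** Two-sided alpha 0.05 and power 0.8 (Table 7). Equal allocation (5.2). 500 households per LA (6.2). 20% attrition (9.2). Test Valley is outside the primary model (5.2 update), so three LAs give 3 × 500 / 2 = 750 randomised per arm. All four LAs would give 1,000.

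**Assumptions.** The alpha of the missingness test is not stated, so 0.05 two-sided is used. Loss of 6% and 10% is shown beside the planned 20%. The base rate is taken as 50%, the level below which the footnote to Figure 3 does not expect outcomes to fall if the model works. The loss mechanisms are illustrative.

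**The protocol's own figure.** Section 9.1 states that "our MDES at alpha = 0.05 and power (beta) = 0.8 is a 2-7 absolute percentage point difference". For Scenario C, 1,000 × 0.8 = 800 analysed per arm. Solving for 80% power gives 6.98 pp at a 50% base rate and about 2.0 pp at 3% or 99%, so 2-7 pp reproduces. With 750 × 0.8 = 600 per arm, the figure at 50% is about 8 pp.

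**Power of the missingness test.** With overall loss m and gap d, the arms lose m − d/2 and m + d/2.

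SE = √{[m₁(1 − m₁) + m₀(1 − m₀)] / n}; power ≈ Φ(d/SE − 1.96).

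Example with n = 750, 18% v 22%: SE = √[(0.1476 + 0.1716)/750] = 0.0206; d/SE = 1.94; power = 49%; miss rate = 51%.

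| Overall loss | Per arm | Miss 3 pp | Miss 4 pp | Miss 5 pp |
|---|---|---|---|---|
| 20% | 750 | 69% | 51% | 32% |
| 20% | 1,000 | 61% | 39% | 20% |
| 10% | 750 | 51% | 27% | 10% |
| 10% | 1,000 | 39% | 15% | 4% |
| 6% | 750 | 31% | 10% | 2% |
| 6% | 1,000 | 19% | 3% | below 1% |

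At 20% loss and 750 per arm, a gap of 5.8 pp is needed for 80% power.

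**Bias from a missed gap.** Suppose there is no true effect, common losses are random, and a share f of the excess missing treated households is homeless. With base rate p and treatment-arm loss m₁:

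bias = −d(f − p)/(1 − m₁).

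- 10% loss, 3 pp gap, f = 1, p = 0.5: −0.03 × 0.5 / 0.885 = −1.7 pp.
- 20% loss, 5 pp gap, f = 1, p = 0.5: −0.05 × 0.5 / 0.775 = −3.2 pp.
- With f = 0.75 both halve, to −0.8 pp and −1.6 pp.

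**Equal loss, arm-specific dependence.** Suppose both arms lose 20%. In control the loss is random. In treatment it is twice as likely among homeless households. At p = 0.5, treated households are lost at 26.7% if homeless and 13.3% if not. The complete-case risk is 0.5 × 0.733 / 0.8 = 45.8%, a bias of −4.2 pp. At p = 0.2 the bias is −3.3 pp. In simulation (1,500 runs per scenario, no true effect, unadjusted tests), the missingness test was non-significant in about 95% of trials, its nominal rate. In those, the primary comparison was falsely significant in about 31-41%. At 10% loss the bias is −1.5 to −1.9 pp and the false-positive rate about 10-13%.

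**Common mechanism.** If loss depends on the outcome in the same way in both arms, the odds ratio is unchanged (0.818 before and after in the case checked).

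**The case against.** Several points on the other side stand.

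- A reader might infer that every check on missing data is switched off. That is too strong. The by-arm description and the re-run without the blocking variable do not depend on the treatment term, and a gap of 3-5 pp would be visible in a report. Neither check, however, addresses outcome-dependent loss.
- The protocol expects little loss (8.2, 9.2, 10.8). Just above the 5% threshold the test is fairly good: at 6% loss it finds a 4 pp gap with 90% power at 750 per arm. The high miss rates belong to 10-20% loss.
- A reader might infer that any outcome-dependent loss at equal rates biases the result. It biases the odds ratio only if the dependence differs by arm. Treatment-only opt-outs added to common losses would also give unequal rates, which the test does examine. Equal rates need an offsetting excess loss in control, and the documents name none.
- Larger biases can be constructed by letting the dependence run in opposite directions in the two arms, but the documents give no reason to expect such a reversal.
- A reader might infer that bias from a missed gap can match the effect the trial is sized to detect. At a 50% base rate, −3.2 pp is under half of the 7-8 pp MDES, and it assumes that every excess missing household is homeless.
- The section says that it follows CHI's guidance, which is not at hand, and an unseen SAP could add scenarios. Neither changes what this section states. The sentence is a rule already fixed, not a detail left open.

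**Conclusion.** The concern holds in a limited form. Section 10.8 wrongly treats a non-significant treatment term as establishing that complete-case analysis is appropriate at any level of loss, and it makes the MENAR bias-reduction, imputation and extreme-value analyses conditional on significance. Only those analyses are gated.

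The size depends on how much is lost. In the primary-model sample, the test misses a 3 pp gap in 69% of trials at 20% loss, 51% at 10% and 31% at 6%. The worst-case bias from such missed gaps is between −1.7 and −3.2 pp at a 50% base rate. The test offers no protection beyond its nominal rate against equal-rate loss whose dependence on the outcome differs by arm. That pattern is possible here but is not shown by the documents.

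These figures assume a two-sided 0.05 missingness test, 500 households in each of three LAs, and the stated mechanisms. The faulty inference does not depend on any of them. The plan should be changed, but the defect does not by itself invalidate the primary analysis.

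**What to change.** Delete the sentence that equates a non-significant treatment term with MEAR, and remove the MENAR condition from the list of methods. A possible replacement:

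*Complete-case analysis with the primary model is the main analysis. Whenever 5% or more of primary outcomes are missing, and whatever the p-value for treatment in the missingness regression, we will report the between-arm difference in missingness with its 95% confidence interval. We will also run the imputation and extreme-value analyses listed below, adding scenarios that differ by arm: missing outcomes set to 1 in one arm and 0 in the other, and the reverse, or a tipping-point version.*

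The arm-specific scenarios are needed because setting all missing outcomes to 1, or all to 0, in both arms does not bound loss that differs by arm. If full bounds prove too wide to be useful, the tipping-point version shows how different the missing households would have to be to change the conclusion.

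The cost is a short addendum before analysis, a route that section 13.2 already provides, and a few lines of code on data already held. The downside is a little more reporting, and possibly wide bounds if loss is high.

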5.2. Study Design

Study design details

The IE is a two-arm parallel RCT with randomisation at the household level, blocked by LA and predicted risk of homelessness. Households in the 'treatment' arm will receive proactive support (in the form of a phone call) from their LA in addition to BAU support. Households in the 'control' arm will only receive BAU support from LAs. This varies between LAs and refers to the range of activities that LAs and local organisations (including the third sector) undertake, and services they offer, to prevent and reduce homelessness. This support is available to households in both

the intervention and control arms, the difference is whether they receive a phone call that signposts them to the relevant support for them.

Allocation

Verian will randomly allocate households into the trial's two arms with equal probability, with a blocking design to ensure that the sample within each LA is as well balanced as possible on predicted risk of homelessness at the trial's start.

To assign blocks, we will independently sort each LA's sample by a continuous risk score generated by Xantura and then sequentially allocate households to blocks of four, following the sorted order. The target sample size at this point will be a multiple of four, so all blocks should be fully filled. If this is not the case, any remaining households will be entered into the final block. Once sorted into blocks, we will randomly assign households within each block so that every block of four contains two treatment households and two control. If the final block contains an odd number of households, we will randomise those households freely. The sample is thus stratified by LA and then risk score within LA.

We will randomise using the R package 'randomizr' (Coppock, 2019). One researcher will conduct the randomisation, but the code will be checked by another researcher to ensure it has been conducted correctly and can be reproduced. Once conducted, the randomisation code will be saved and made available in the OSF pre-registration that will be published for this trial.

Batching

We will deliver the sample to LAs in three batches, at the start of the first, second, and third months of the trial. We will run the randomisation separately for each batch, using up-to-date risk scores generated by Xantura.

Update to protocol: Study design in Test Valley

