8. DATA COLLECTION

8.1. Data collection methods

All study outcomes and planned covariates come from administrative records, which will be provided by LAs on a monthly basis and collated within the OneView platform. Additionally, call handlers will use OneView to record their attempts and success at making the treatment calls to support the compliance analysis and IPE. Xantura will have responsibility for managing data collection, ensuring data quality, and minimising missing information. They will provide household-level risk scores for the randomisation and then will deliver outcome data at the 2-month and 9-month follow-ups.

Timelines

For each batch, the trial will begin with randomisation, followed by a 1-month intervention period in which LAs deliver the calls to treatment households, with the two follow-up data collection points occurring 2 and 9 months after the end of the intervention period.

Table 6: Data collection procedures and assessment timeline

Assessment point	Type of data	Data collection approach
Pre-trial Batch 1: April 2025 Batch 2: May 2025 Batch 3: June 2025	Baseline characteristics of the sample All administrative data from LAs Risk scores from Xantura's predictive model (for randomisation)	Data collected from LA records by Xantura via OneView
1-month Intervention period Batch 1: May 2025 Batch 2: June 2025 Batch 3: July 2025	Outcomes related to the proactive call made to individuals in at risk households.	Data collected from LA call handlers by Xantura via OneView
2-month follow-up Batch 1: July 2025 Batch 2: August 2025 Batch 3: September 2025	Secondary outcome data	Data collected from LA records by Xantura via OneView

9-month follow-up Batch 1: February 2026 Batch 2: March 2026 Batch 3: April 2026	Primary outcome data Secondary outcome data	Data collected from LA records by Xantura via OneView
---	--	---

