- Three approaches to imputing outcomes: using those from other cases within the same block and testing the extremes of imputation by replacing all missing values with 1s or all with 0s.

Attrition at the LA level

In the event of data being missing from an entire LA because that LA withdraws from the trial, imputation would not be possible and that LA would be excluded from all analyses.

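### Within-block imputation, as worded, takes two of three donors from the opposite arm and pulls the effect toward zero in a conditional sensitivity analysis

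*Protocol*

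**What the plan says.** Protocol section 10.8 uses complete cases if fewer than 5% of outcomes are missing, or if treatment does not significantly predict missingness. Otherwise it will try and report several methods intended to reduce bias: dropping blocks with missing data, adding household covariates, and a group described as "Three approaches to imputing outcomes: using those from other cases within the same block and testing the extremes of imputation" (all 1s, all 0s). No donor arm is specified.

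The section explains why it does not use other imputation: "The imputation methods preferred in CHI's guidance are not possible, since they depend on baseline measures that won't be present in this study".

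Section 5.2 says that households are allocated 1:1 and that "every block of four contains two treatment households and two control". Table 6 in section 8.1 lists, as collected before the trial, "Baseline characteristics of the sample All administrative data from LAs" together with the risk scores. Section 10.2 will describe the risk factors behind the scores. Section 10.8 itself notes that the model predictors must be present for every enrolled household.

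**The concern.** Blocks were built to balance the arms, so they mix the arms by design. Filling a missing treatment outcome from the rest of its block mostly copies control outcomes into the treatment arm, and the reverse. A method introduced to reduce bias then adds its own, always toward no effect, and does so in the situation where readers look to it for reassurance. A real effect could seem to fade once missing data are handled, purely because of the donor rule.

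The other two imputation runs are deliberate extremes, so as written the plan has no central imputation that respects arm. The text also describes single filled values, with no step for the uncertainty of filling.

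**Working it through.** **Plan's own figures.** Section 9.2 states that "Scenario C will represent the expected main scenario at the time this protocol is first registered". Scenario C randomises 2,000, and 2,000 × (1 − 0.20) = 1,600, as in Table 7. With 800 per arm, two-sided alpha 0.05 and power 0.80, the detectable difference at a 50% base rate is 6.98 percentage points, which agrees with the upper end of the stated 2–7. I use 7.0 points as the illustrative true effect. The protocol gives no figure for the bias from block imputation.

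**One missing household.** Let the true risk difference be d, and the loss be mT (treatment) and mC (control). A missing treatment household has three possible donors, one treatment and two control. Its expected filled value is the control risk + d/3, where it should be the control risk + d. So:

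- the treatment mean moves by mT × (2/3) × d toward control;
- by symmetry, the control mean moves by mC × (2/3) × d toward treatment;
- the share of d lost is about (2/3) × (mT + mC).

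**Exact check.** I enumerated all 16 missingness patterns in a block of two plus two. Each missing outcome takes the mean of the observed others, and wholly missing blocks are dropped. Missingness is taken as unrelated to outcome within arm, which isolates the effect of the donor rule.

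| Loss T/C (assumed) | Overall | Formula: share lost | Exact: share retained | 7.0 points becomes |
|---|---|---|---|---|
| 10%/5% | 7.5% | 10.0% | 0.899 | 6.3 |
| 15%/5% | 10% | 13.3% | 0.863 | 6.0 |
| 25%/15% | 20% | 26.7% | 0.732 | 5.1 |

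The result is the same with the arms swapped. With equal arms the formula equals (4/3) × overall loss, so at the 5% threshold the shrinkage is already about 6.7%.

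**Would these splits trigger the run?** Each has at least 5% missing overall. Taking three LAs (Test Valley is left out of the primary model) at 500 each gives 750 per arm. For 10%/5%, the standard error of the difference is √[(0.10 × 0.90 + 0.05 × 0.95)/750] = 0.0135, so z = 0.05/0.0135 = 3.7. The same formula gives z = 6.5 for 15%/5% and 4.9 for 25%/15%. All three would trigger.

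**Does the filling method matter?** Simulations with a random donor, the block mean or the block mode, at 20% loss in each arm, retained 0.71 to 0.75 of the effect. Donors from the same arm retained 0.98 to 1.00. The cross-arm donors are therefore the cause.

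**The case against.** **It rarely bites, and not on the main result.** This stands. Equal 20%/20% loss would go to complete-case analysis, because treatment would not predict missingness. The headline intention-to-treat analysis uses households with an observed outcome. The block run would appear beside four others, so it would not pass alone as the answer to missing data.

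**Twenty percent is a high figure.** This also stands. Section 9.2 plans "with 20% lost as post-randomisation attrition" but adds "We expect such instances to be few, so the figure of 20% is likely to be conservative". A reader might infer that the plan loses a quarter of its effect at its expected attrition. The documents do not support that. The 27% case needs 20% overall loss and a differential split that I assumed, and shrinkage near 10% is the more realistic order if losses are few.

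**The guidance is not at hand.** A reader might infer that the sentence ruling out the preferred imputation methods contradicts Table 6. The documents do not prove it. The sentence concerns methods in guidance that is not reproduced, and it may mean a baseline value of the outcome itself. What does stand is narrower: risk score, LA and household risk factors are available, and they are enough for an imputation model.

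**Donor choice is analysis-plan detail.** Partly fair, since the authors may have intended same-arm donors. But the protocol does fix the donor pool as the block, and nothing in the text limits it to one arm.

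**The check assumes missingness unrelated to outcome within arm, where complete cases are already unbiased.** True. The check shows the bias that the donor rule adds. It does not show how well any method would repair outcome-related loss.

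**Precision.** The primary model clusters standard errors by block, which would pick up some of the dependence created by copying within a block. I therefore put no figure on the understatement of uncertainty.

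**Conclusion.** The point holds for one conditional sensitivity run. Followed as written, within-block imputation shrinks the estimated risk difference by about 10% at 10%/5% loss, 14% at 15%/5% and 27% at 25%/15%. It also treats single filled values as observed. This rests on donors being drawn from both arms, on full blocks of two plus two, on missingness unrelated to outcome within arm, and on assumed loss splits.

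It does not bias the headline complete-case estimate, and it is not the expected loss of effect under the plan. The correction is cheap and worth making before analysis, because the run is meant to reduce bias and as worded it adds some.

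**What to change.** Replace the within-block run with multiple imputation of the primary outcome, done separately by arm. Use risk score, LA, batch and the baseline risk factors already supplied, with the 2-month secondary outcomes where available, and combine the results by Rubin's rules. If a block-based run is kept, state that donors come from the same arm, in the same block or an adjacent one when the same-arm partner is also missing. Keep the all-1s and all-0s runs as extremes.

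Reword the sentence on the funder's guidance: its preferred methods may need a baseline value of the outcome, but imputation from the available baseline covariates is feasible.

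The cost is a short addendum, which section 13.2 provides for before any analysis, and a little more analysis work. No new data are needed. The price in assumptions is reliance on data being missing at random given arm and covariates, which should be stated.
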